# Study Procedure

Informed consent will be obtained by one of the investigators or informed consent delegates. The subject will then be assigned randomly to the control (oxytocin alone) or the study (oxytocin + misoprostol) group, as described above. The subject and her medical caretakers will be informed of which group she is in. If the labor eventuates in a vaginal delivery, all subjects will receive the standard dose of intravenous oxytocin, begun within one minute of delivery. Subjects in the study group who have not incurred any of the post-hoc exclusion criteria (episiotomy, major laceration, etc) will receive a dose of 600 µg of misoprostol in addition to their oxytocin. This will be administered in the form of six 100 µg tablets inserted approximately 2 cm into the anorectal canal by the obstetrician or midwife who has performed the delivery. The common method for administering Misoprostol for postpartum hemorrhaging is rectally for local absorption. Since this study is directed toward prevention instead of treatment, the dosage of 600mg is a lower dosage from the 1000mg administered, as standard practices, for treating postpartum hemorrhaging of more than 500cc estimated blood loss. patient's vital signs will be recorded after delivery according to standard protocols of the obstetric service. The Data Collection forms will be filled out after the delivery by one of the investigators. The measurement of postpartum hemoglobin and hematocrit (H & H) is automatically ordered at 06:00am for all patients who have delivered the day prior, constituting this measurement at "Postpartum Day 1", which is at a minimum of 6 hours after delivery and is enough time for H & H levels to stabilize.

Within 36 hours of delivery, additional information will be collected from the patient's record, including the postpartum hemogram and information about any symptoms or signs related to the misoprostol.

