#### Inclusion and exclusion criteria

This study will include adult pregnant women regardless of age. Pregnant minors under the age of 18 will not be eligible.

A patient will be considered for inclusion in the study if she meets all of the following criteria:

- She has a term (≥37 completed weeks) live singleton gestation in cephalic presentation and has been admitted to the Labor and Delivery Unit
- She is in the latent phase of labor or has been admitted for induction of labor or at prenatal clinic visit
- She has had fewer than four prior vaginal deliveries.
- She reports no allergy to misoprostol.

The following factors or conditions will exclude a patient from consideration as a subject:

- The fetus has a known major fetal malformation or chromosome abnormality
- The gestation is multiple.
- There is a breech or other malpresentation
- The patient reports involvement in another clinical trial currently or previously in this pregnancy.
- The patient is expected to have a cesarean delivery.
- The patient had a prior cesarean delivery.
- There has been an intrauterine fetal death.
- There is polyhydramnios (amniotic fluid index >22 cm).
- Presence of acute or chronic renal disease
- Presence of preeclampsia

Of subjects who enter the study, the development of certain conditions will exclude them post hoc from receiving misoprostol under the protocol, and from the data analysis. These conditions include:

- Unanticipated cesarean delivery.
- Performance of episiotomy (third and fourth degree extensions will be excluded).
- Vaginal or cervical laceration, or perineal laceration of more than second degree in depth.
- Severe postpartum hemorrhage requiring intervention immediately after delivery.
- Uterine rupture
- Placental abruption.
- Patient withdrawal of consent.

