#### Recruitment and Consent Procedures

Patients who meet the inclusion criteria for the study will be identified during their prenatal clinical visits, in early latent-labor, or prior to induction of labor or active labor. Informed consent will be obtained by one of the investigators. Consent will be obtained prior to active labor. The informed consenting process will not be initiated among patients in active labor. Patients will be recruited and consented with the consent document approved by the IRB. Patient recruitment will commence after IRB approval is obtained.

Once the subject has consented to participate in the study, it will be determined by the investigator whether the patient will receive oxytocin alone or oxytocin and misoprostol. Both drugs are on formulary and will be available on the Labor and Delivery Unit for immediate use.

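### The arm is assigned after consent and, as the text reads, disclosed before delivery, so the events that later remove women from the analysis can depend on the known arm

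*Combined protocol and SAP*

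**What the plan says.** Recruitment and Consent Procedures: "Consent will be obtained prior to active labor". Then: "Once the subject has consented to participate in the study, it will be determined by the investigator whether the patient will receive oxytocin alone"; the alternative is the combination with misoprostol.

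Study Procedure repeats that order (consent, then random assignment) and continues: "The subject and her medical caretakers will be informed of which group she is in". The next sentence is: "If the labor eventuates in a vaginal delivery, all subjects will receive the standard dose of intravenous oxytocin, begun within one minute of delivery". Study-group women with none of the post-hoc conditions then also receive misoprostol. On recording: "The Data Collection forms will be filled out after the delivery by one of the investigators".

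Inclusion and exclusion criteria states that, among women who have entered, "the development of certain conditions will exclude them post hoc from receiving misoprostol under the protocol, and from the data analysis". Seven conditions follow. They include "Unanticipated cesarean delivery", episiotomy, certain lacerations, "Severe postpartum hemorrhage requiring intervention immediately after delivery" and withdrawal of consent; uterine rupture and placental abruption complete the list.

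Randomization describes sequentially numbered sealed envelopes in a locked file in the Labor and Delivery area. It does not say when in the course of labor an envelope is opened.

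**The concern.** Nothing that differs between the arms happens until after a vaginal birth. If the arm is known during labor, the woman and her caretakers pass through several decisions and judgements with that knowledge. Cesarean and episiotomy are operator decisions. Laceration depth and the severity of a hemorrhage are graded at the bedside. Withdrawal is the woman's own choice. Each of these removes her from the analysis.

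If removal differs by arm, the analysed groups are no longer those that randomisation created, and the hemoglobin comparison can move without any drug effect. Severe hemorrhage matters most because it lies closest to the outcome. The postpartum sample is ordered automatically at 06:00, which limits measurement bias but does not govern who is analysed. Open-label treatment is declared and is not the complaint; the complaint is when the arm becomes known, combined with removal from the analysis.

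**Working it through.** **Order of events**

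1. Consent precedes active labor, and assignment follows consent (Recruitment and Consent Procedures; Study Procedure).
2. Disclosure comes next in Study Procedure. The sentence after it is conditional on the labor ending in vaginal delivery, which makes sense only if the mode of delivery is still unknown.
3. The exclusions arise in women who have already entered the study.
4. No clock time is given, so disclosure before delivery is an inference from this order. The window may be short. The first inclusion criterion requires admission to the unit, while the second allows a prenatal clinic visit, so it is unclear when a woman consented in clinic is assigned.
5. No section delays disclosure, has the exclusions judged without knowledge of arm, or provides for analysis as assigned.

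**Recording of the exclusions.** The After Delivery list carries four of the seven conditions as items: cesarean, episiotomy, laceration and abruption. Severe hemorrhage appears only indirectly, through estimated blood loss and transfusion. Uterine rupture and withdrawal are absent. Study Procedure describes a check of the conditions before dosing for study-group women only; no matching check at that moment is described for controls. The form is completed when the arm is already known.

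**The plan's own figure.** For a difference of 0.3 g/dL, SD 1.3 g/dL, two-sided 0.05 and 90% power, n per arm = 2 × (1.3/0.3)² × (1.960 + 1.282)² = 395 after rounding up, or 790 in total against the planned 800. Power with 400 per arm is 90.4%. The plan's figure reproduces.

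**Scale of a possible bias (assumed inputs).** The documents give no exclusion rate, no difference by arm and no excess fall. Assume:

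- 20% of the 800 are excluded, leaving 640, or 320 per arm;
- one arm loses an extra share q of its otherwise analysable women;
- those women have a hemoglobin fall larger by d than the rest;
- the true effect is zero;
- the arms are compared by a two-sample t-test (Sample size and analysis names only a paired test).

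The arm that keeps these women has a mean fall larger by q × d, so the spurious shift is q × d.

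Two SDs are used. One is 1.3 g/dL, the upper bound in Sample size and analysis. The other is the SD of the change implied by Preliminary Data: half-width (1.29 − 0.74)/2 = 0.275; 0.275/2.007 × √53 = 1.00 g/dL.

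The standard error is SD × √(2/320), which is 0.079 or 0.103. Rejection rates at two-sided 0.05 come from the noncentral t with 638 degrees of freedom and noncentrality shift/SE.

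| q (women of 320) | d, g/dL | Shift, g/dL | P<0.05, SD 1.0 | P<0.05, SD 1.3 |
|---|---|---|---|---|
| 2% (about 6) | 0.5 | 0.010 | 5.2% | 5.1% |
| 5% (16) | 0.5 | 0.025 | 6.1% | 5.7% |
| 10% (32) | 0.5 | 0.050 | 9.7% | 7.7% |
| 2% (about 6) | 1.0 | 0.020 | 5.7% | 5.4% |
| 5% (16) | 1.0 | 0.050 | 9.7% | 7.7% |
| 10% (32) | 1.0 | 0.100 | 24.4% | 16.3% |

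If d = 0 there is no shift. With d = 1 the shifts are 7%, 17% and 33% of the 0.3 g/dL target. Allowing for the unequal arm sizes (320 against 314, 304 or 288) changes the d = 1 rates little: 5.7%, 9.6%, 23.3% (SD 1.0) and 5.4%, 7.7%, 15.7% (SD 1.3).

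**The case against.** The strongest reply has five parts.

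- **Timing is inferred.** The envelopes are kept on the unit and one criterion requires admission, so the window may be short. This stands as a limit on confidence, but no passage places disclosure after birth.
- **Open label is declared**, and the person delivering must know the arm around birth in order to give the tablets. True, but that requires disclosure after birth, not during labor.
- **The events are unevenly exposed.** The documents give no reason why a single dose after birth would change a cesarean or episiotomy decision, and abruption and rupture are hardly open to influence. This stands in part. Withdrawal and the labelling of a severe hemorrhage remain plausible routes.
- **Severe hemorrhage is not only a timing problem.** It may be recognised after dosing and may be affected by the drug. This stands: later assignment alone does not close that route, so the fix must also keep randomised women in the analysis.
- **The magnitude is wholly assumed.** The 10% and 1 g/dL case needs all 32 extra losses to average that excess. If only 2 percentage points of the 10% had it and the others none, the shift would be 0.02 g/dL and the rejection rate about 5.7% (SD 1.0) or 5.4% (SD 1.3). This also stands. A 1 g/dL excess may fit severe hemorrhage; nothing in the documents supports it for withdrawal or lacerations.

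**Conclusion.** The concern holds. Followed as written, the plan makes the arm known before the events that decide who is analysed, and it has no as-assigned analysis to protect the comparison. This is a risk of bias, not a demonstrated bias: its size and direction cannot be derived from the documents. Across the assumed cases it runs from almost nothing to one third of the target difference, and the upper end should be read as an extreme. Confidence is medium, because the timing is read from the order of the text and the inputs for size are assumptions. The plan should be changed, since the early assignment serves no stated purpose and later analysis cannot fully repair selection that depended on arm.

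**What to change.** Keep consent before active labor. Open the next envelope only after vaginal birth, once the exclusion conditions have been checked and recorded for every consented woman, and before misoprostol would be given. Disclose the arm only then. Oxytocin and all other care common to both arms do not wait for the envelope; only misoprostol does, and the plan sets no time limit for it. Amend:

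- **Recruitment and Consent Procedures:** the time of assignment.
- **Randomization:** who opens the envelope; strict sequence; study number (already given at consent under Confidentiality), date and time written on the envelope before opening.
- **Study Procedure:** the sequence and the moment of disclosure.
- **Inclusion and exclusion criteria:** conditions found before opening prevent randomisation. Women already randomised, including those whose hemorrhage is recognised later, stay in the analysis as assigned wherever a postpartum hemoglobin exists and consent to use it stands.
- **Sample size and analysis:** the 800 are women randomised at that point.
- **After Delivery form:** add severe hemorrhage requiring intervention, uterine rupture and withdrawal.

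The cost is one amendment to five sections and three form items, with no new drug, test or visit. An envelope must be opened soon after birth at any hour. Wider access to the locked file is a concealment risk, which the strict order and prior labelling limit but do not remove. More women must be consented: 800/(1 − loss) gives 889, 1,000, 1,143 or 1,334 if 10%, 20%, 30% or 40% never reach randomisation (assumed rates).

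If the timing cannot move, analyse all randomised women with a postpartum hemoglobin as assigned, and report exclusions and missing values by arm and reason. This is lighter but weaker. Withdrawals and missing values can still differ by arm, arm-dependent delivery care is untouched, and untreated women enter the comparison.

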## Confidentiality

After a subject has given informed consent, she will be assigned a Study Number. This number will be used on the study data collection form as the sole patient identifier, i.e., the form will not contain the subject's name or hospital number. A single hard copy list of the subjects' Study Numbers and their medical record numbers will be kept in a locked cabinet in the Principal Investigator's sponsor's office ([name]). This list will be destroyed once the study has been accepted for publication. Only [name] will have access to this list.

#### Costs

The cost of each  $600 \mu g$  dose of misproostol will be \$4.80. There will be no charge to the patient. The drug will be paid for through the research fund of the Department of Obstetrics and Gynecology at Queens Hospital Center.

#### **Data Collection**

Data collection will include the following elements:

#### **Before Delivery**

- Age
- Ethnicity/Race
- Gestational age (in weeks)
- Number of previous deliveries
- Number of Fetus
- Body-Mass Index (BMI)
- Amniotic Fluid Index (AFI)
- Cephalic presentation
- Fetal Heart Rate (FHR)
- Reported fetal Anomaly

- Preeclampsia
- Trial of Labor after Cesarean (TOLAC)

#### After Delivery

- Caesarean section (during delivery)
- Epidural
- Oxytocin in labor (if yes, number of hours before delivery
- Other medication used in labor
- Episiotomy
- Duration of stage 1, 2, and 3
- Degree and place of laceration
- Estimated Blood Loss (EBL)
- Transfusion
- Placental Abruption
- Birth weight

#### Results – includes Follow-up Data

- Hemoglobin and Hematocrit (H& H) on admission and on post- partum day #1
- Reported Side effect by patient
- Post partum temperature
- · Reports of shivering
- Diagnosis of chorioamnionitis

Post- partum day #1- data collection

Postpartum Day 1 is delineated as the first 12:01am clock time from the time of delivery. Post-partum measurements, such as postpartum hemoglobin and hematocrit (H & H), are taken automatically at 06:00am for all deliveries that occurred before midnight (at least 6 hours prior).

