The use of misoprostol to enhance uterine activity postpartum is an off-label method, but one that has gained wide acceptance, and for which there is considerable experience.[8-10, 12-19] The drug can cause nausea, headache, dyspepsia, vomiting, and constipation or diarrhea with multiple doses. These side effects are usually mild to moderate and generally subside within a week. Serious side effects after a single dose are quite rare. In one study of 327 women who received 600 µg rectally (the dose we propose to use), the most common side effects were transient shivering (26%) and pyrexia (15%). Both were mild and short-lived. [16]

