# Benefits and Risks to Study Subjects

There will be no certain medical benefit to the subjects who participate in the study. It is possible that they will benefit from reduced postpartum blood loss.

Risks to the subjects are those associated with administration or misoprostol.

These include the following adverse events that have been reported in subjects receiving misoprostol for ulcer prophylaxis: diarrhea, abdominal pain, nausea, flatulence, headache, dyspepsia, vomiting, and constipation. All occurred in fewer than 5% of patients. Other reported effects that occurred in clinical trials of misoprostol, but for which no cause-effect relation has been established included fatigue, fever, chills, rash, alopecia, pallor, breast pain, abnormal taste, abnormal vision, conjunctivitis,

deafness, tinnitus, earache, chest pain, edema, diaphoresis, hypotension, hypertension, arrhythmia, phlebitis, increased cardiac enzymes, syncope, myocardial infarction, thromboembolism, abnormal hepatobiliary function, gingivitis, reflux, dysphagia, gout, polyuria, dysuria, hematuria, urinary tract infection, anxiety, depression, and thrombocytopenia. As with any drug, anaphylaxis is possible.

We emphasize that in a number of published studies using a single postpartum dose of misoprostol of  $600-1000~\mu g$  and including in aggregate in excess of 1000~patients, no serious side effect has been reported.

Side effects after a single dose of misoprostol are rare. Misoprostol can cause nausea, headache, heartburn, vomiting, flatulence, and constipation or diarrhea with multiple doses. These side effects are usually mild to moderate and generally go away within a week. Mild shivering and slight fever are the most likely side effect of this medication. If they occur, they will probably disappear within an hour.

Oxytocin commonly causes vomiting and nausea. Oxytocin has the potential to cause muscle contractions. In rare cases, Oxytocin can cause heart palpitations (rapid heartbeat) and allergic reaction of a rash or swelling.

It is unknown whether Misoprostol and/or Oytocin are excreted in human milk. There is an unconfirmed relation with Misoprostol and/or Oytocin causing digestive problems, such as diarrhea, and abdominal cramps in breast-fed newborns. Pariticipants will be advised to discard breast mild for the first 24 hours to possibly avoid occurrence.

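### Postpartum temperature is recorded as one untimed value, so a Day 1 reading may miss much of the brief fever expected from misoprostol

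*Combined protocol and SAP*

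**What the plan says.** **The form item.** Under Results – includes Follow-up Data, temperature appears only as "Post partum temperature". No time, window, method, choice of reading or definition of fever is attached. The hemoglobin and hematocrit line in the same list does carry a time (admission and Day 1).

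**The stated measurement time.** The Day 1 paragraph in that section says: "Post-partum measurements, such as postpartum hemoglobin and hematocrit (H & H), are taken automatically at 06:00am". It applies this to births before midnight, at least 6 hours earlier, and starts Day 1 at the first 12:01am after delivery.

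**The expected fever.** The medication section cites a study of 327 women given the same rectal dose, with shivering in 26% and pyrexia in 15%, both mild and brief. Benefits and Risks to Study Subjects names mild shivering and slight fever as the likeliest side effects and adds: "If they occur, they will probably disappear within an hour".

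**Other routes to the information.** Study Procedure says that "vital signs will be recorded after delivery according to standard protocols of the obstetric service". It also has the record reviewed within 36 hours of delivery for symptoms or signs linked to misoprostol. The form has separate lines for patient-reported side effects, shivering and "Diagnosis of chorioamnionitis", all untimed.

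**Before delivery.** Neither the Before Delivery nor the After Delivery list includes a maternal temperature.

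**The concern.** Fever is the second most common effect the protocol expects from adding misoprostol, and one of the few harms with its own line on the form. The protocol expects it to be brief, yet the only measurement time stated beside that line is many hours later. If the Day 1 value is entered, the two arms could look more alike on fever than they were.

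The remaining route has a different weakness. The chart review asks for signs related to a drug that control women do not receive, and Study Procedure tells the woman and her caretakers which group she is in. A fever in the misoprostol arm is then more likely to be written down as a side effect than the same fever in the control arm. A late reading would shrink the difference, and drug-attributed collection could inflate it. Neither gives a like-for-like comparison of a harm that the trial is large enough to measure.

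**Working it through.** **1. The plan's own sample size.** The inputs, from Sample size and analysis, are a difference of 0.3 g/dL, SD 1.3 g/dL, two-sided 0.05 and 90% power.

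n per arm = 2 × (1.960 + 1.282)² × 1.3² / 0.3² = 394.6, rounded up to 395, or 790 in total.

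The plan states 800, so its figure is reproduced (power at 400 per arm is 0.904). The plan gives no sample size, power or comparison for fever.

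**2. Interval from birth to the 06:00 measurement.** By the Day 1 definition, a birth just before midnight is measured about 6 hours later. A birth just after midnight waits about 24 hours for the next 12:01am and 6 more to 06:00, about 30 hours in all. The protocol expects fever probably to be gone within an hour. A reading at 6 to 30 hours lies well outside that.

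**3. Number of women affected.** 0.15 × 400 = 60. The 400 assumes equal allocation of the 800. It is a ceiling, because cesarean, episiotomy, major laceration and the other post-hoc criteria withhold misoprostol from some women.

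**4. Does the text fix which temperature is entered?**

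| Statement | Effect on temperature |
|---|---|
| Form line for temperature | No time or choice of reading |
| Day 1 paragraph, 06:00 | Hemoglobin and hematocrit are given as examples; temperature is neither named nor ruled out |
| Study Procedure, 06:00 order | Hemoglobin and hematocrit only |
| Study Procedure, vital signs | Charted after delivery; schedule not given |
| Study Procedure, 36-hour review | Signs attributed to misoprostol |

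Early readings may be in the chart, but nothing says that one of them goes on the form.

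**5. What incomplete capture would cost (illustration).** Let c be the share of drug-related fever captured and pC the control fever rate. Both are assumptions. The recorded rate in the misoprostol arm is pT = pC + c × (0.15 − pC). With n = 400 per arm and p̄ the mean of the two rates:

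power = Φ{ [ (pT − pC) − 1.96 × √(2p̄(1 − p̄)/n) ] / √[ (pT(1 − pT) + pC(1 − pC))/n ] }

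Example with c = 0.5 and pC = 0.03: pT = 0.09 and p̄ = 0.06. The two standard errors are 0.01679 and 0.01666. Then (0.06 − 0.0329)/0.01666 = 1.63, giving power 0.948.

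| Capture c | pC = 1% | pC = 3% | pC = 5% |
|---|---|---|---|
| 100% | 1.00 | 1.00 | 0.997 |
| 50% | 0.998 | 0.948 | 0.767 |
| 25% | 0.858 | 0.535 | 0.309 |
| 10% | 0.334 | 0.147 | 0.090 |

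The true c cannot be computed from the documents. The table shows only that 400 per arm is ample if fever is well captured and inadequate if little of it is.

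**The case against.** The strongest reply is that the protocol never says temperature is taken at 06:00, or only once. The operative sentence in Study Procedure covers blood tests alone: "The measurement of postpartum hemoglobin and hematocrit (H & H) is automatically ordered at 06:00am for all patients who have delivered the day prior". Vital signs are charted after delivery, the record is reviewed within 36 hours for misoprostol-related signs, and patients' own reports are collected. Fever is plainly such a sign, so an early fever can reach the trial data.

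Much of this stands. A reader might infer that the trial will miss its misoprostol fevers, and the documents do not support that. They leave the choice of reading open, and the one-hour duration is itself hedged with a probably. What the reply does not supply is a rule for which charted value is transcribed, or a collection that works the same way in both arms. A slight fever may also go unnoticed by the woman, so self-report is no substitute.

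Three further inferences should be resisted:

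- **Infection as a confounder.** A reader might think intrapartum infection confounds the fever comparison. Assignment is random and follows consent, which is obtained before active labor, so such fever should be similar in both arms on average. It adds background and blurs attribution in individual women, but does not by itself bias the difference.
- **Half-life as proof.** The 20 to 40 minute half-life might seem to show that fever is gone by 6 hours. That figure is given for oral dosing, and it describes drug level rather than how long fever lasts.
- **A false safety conclusion.** A reader might say the trial would declare misoprostol free of fever. The analysis section plans only hemoglobin and hematocrit comparisons, so no such conclusion is specified.

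**Conclusion.** The point holds as a weakness in how an expected harm is measured. Temperature is a single untimed value beside a stated measurement time of 6 to about 30 hours after birth, while the protocol expects the fever probably to last under an hour. A Day 1 reading may therefore miss much of it.

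At most about 60 treated women are concerned, resting on the cited 15%, equal allocation and no post-hoc exclusions. The shortfall could run from none, if early charted readings are used, to nearly all, if only a late reading is entered and the fevers have resolved. The documents do not say where in that range the trial would fall. The chart review narrows the gap but may do so unequally between arms. The hemoglobin comparison is unaffected.

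**What to change.** In Results – includes Follow-up Data, replace the temperature line with items abstracted identically in both arms from vital signs already charted:

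- the last temperature charted before delivery;
- the highest temperature charted from delivery over a fixed window that includes the first hours, with its clock time.

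State one fever threshold in advance. Report new fever after delivery by arm, meaning women at or above the threshold afterwards who were below it before.

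Optionally, note whether chorioamnionitis was diagnosed before or after delivery. This helps attribution in individual women and is not needed to remove bias between arms.

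The cost is a few form fields and a little abstraction time, with no new measurement or visit. Because the ward schedule is not stated, the sponsor should confirm that it includes a temperature in the first hours in both arms. If it does not, the new item would share the present weakness.
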